## 3.0 STUDY OBJECTIVES AND ENDPOINTS

## 3.1.1 Primary Study Objectives and Endpoints

Objective	Endpoint	
■ To investigate safety and tolerability of  Cu-SAR-bisPSMA.	■ Incidence and severity of treatment-emergent adverse events (AEs) and serious AEs (SAEs) following the administration of  Cu-SAR-bisPSMA.	
To investigate the ability of 64Cu-SAR-bisPSMA PET/CT to correctly detect recurrence of PC.	■ Participant-level correct detection rate (CDR), defined as the proportion of true positive (TP) participants on the Day 0 scan out of all participants with a Day 0 scan.	
	
 
Participant-level CDR, defined as the proportion of TP participants on the Day 1 scan out of all participants with a Day 1 scan.
 
	
	Region-level positive predictive value (PPV), defined as the proportion of TP regions on the Day 0 scan out of all positive regions on the Day 0 scan.	
	
 
Region-level PPV, defined as the proportion of TP regions on the Day 1 scan out of all positive regions on the Day 1 scan.
 
	

## 3.1.2 Secondary Study Objectives and Endpoints

Objective	Endpoint	
■ To investigate the biodistribution of  Cu-SAR-bisPSMA.	
 
Biodistribution of Cu-SAR-bisPSMA on the Day 0 and Day 1 scan:
 
Maximum and mean standardized uptake values (SUVs) in lesion(s), visceral/soft tissue, bone.
 
Lesion-to-background ratio.
 
	
■ To assess the participant-level positive predictive value (PPV) of  Cu-SAR-bisPSMA PET/CT.	
 
Participant-level positive predictive value (PPV), defined as the proportion of TP participants on the Day 0 scan out of all participants with a positive Day 0 scan.
 
	

September 4, 2024 CONFIDENTIAL Page 11 of 46

	
 
Participant-level PPV, defined as the proportion of TP participants on the Day 1 scan out of all participants with a positive Day 1 scan.
 

■ To assess the participant-level detection rate (DR) of  Cu-SAR-bisPSMA PET/CT.	
 
Participant-level detection rate (DR), defined as the proportion of participants with a positive Day 0 scan out of all participants with a Day 0 scan.
 
Participant-level DR, defined as the proportion of participants with a positive Day 1 scan out of all participants with a Day 1 scan.
 

To assess the false positive rate (FPR)  Cu-SAR-bisPSMA PET/CT.	
 
Participant-level false positive rate (FPR), defined as the proportion of FP participants on the Day 0 scan out of all participants with a positive Day 0 scan.
 
Participant-level FPR, defined as the proportion of FP participants on the Day 1 scan out of all participants with a positive Day 1 scan.
 
Region-level FPR, defined as the proportion of FP regions on the Day 0 scan out of all positive regions on the Day 0 scan.
 
Region-level FPR, defined as the proportion of FP regions on the Day 1 scan out of all positive regions on the Day 1 scan out of all positive regions on the Day 1 scan.
 

■ To assess the rate of discrepant PET negativity rate of the  Cu-SAR-bisPSMA PET/CT scans.	
 
Participant-level discrepant PET negativity rate, defined as the proportion of participants with contradicting Day 0 and Day 1 results for whom the Reference Standard was positive.
 

To assess the true negative rate (TNR) of  Cu-SAR-bisPSMA PET/CT.	
 
Participant-level true negative rate (TNR), defined as the proportion of TN participants on the Day 0 scan out of all participants with a negative Day 0 scan.
 
Participant-level TNR, defined as the proportion of TN participants on the Day 1 scan out of all participants with a negative Day 1 scan.
 
Region-level TNR, defined as the proportion of TN regions on the Day 0 scan out of all negative regions on the Day 0 scan.
 

September 4, 2024 CONFIDENTIAL Page 12 of 46

•	Region-level TNR, defined as the proportion of TN
	regions on the Day 1 scan out of all negative regions
	on the Day 1 scan.

## 3.1.3 Exploratory Study Objectives and Endpoints

Objective	Endpoint		
To evaluate the reproducibility of the  Cu-SAR-bisPSMA PET/CT readings and consistency among readers.	
 
Intra-reader variability per reader.
 
Inter-reader variability expressed by kappa statistics.
 
		
■ To assess the impact of  Cu-SAR-bisPSMA PET/CT on disease management.	
 
Proportion of participants with any change in intended PC treatment due to either the Day 0 or Day 1 scan.
 
		

 
Composite performance of the Day 0 and Day 1 Cu-SAR- bisPSMA PET/CT scans.
 
	Composite CDR defined as the proportion of TP participants on the Day 0 and/or Day 1 scan out of all participants with a Day 0 and/or Day 1 scan.		
	
 
Composite participant/region-level PPV defined as the proportion of TP participants/regions on the Day 0 and/or Day 1 scan out of all participants/regions with a positive Day 0 and/or Day 1 scan.
 
		
	
 
Composite DR defined as the proportion of participants with a positive Day 0 and/or Day 1 scan out of all participants with a Day 0 and/or Day 1 scan.
 
		
■ To determine the effect of baseline variables on the CDR, PPV and DR of  Cu-SAR-bisPSMA PET/CT.	
 
CDR, participant- and region-level PPV and DR of the Day 0 and/or Day 1 scan as a function of baseline variables.
 
		
■ To explore the correlation between  Cu-SAR-bisPSMA PET-positivity and Reference Standard results.	
 
Relationship between PET-positivity (biodistribution measures such as SUVs and lesion-to-background ratio), versus true/false positivity and as a function of lesion location and size.
 
		

September 4, 2024 CONFIDENTIAL Page 13 of 46

- To assess the lesion-level performance of Cu-SARbisPSMA PET/CT.
- Difference in the number of lesions detected per participant on the Day 0 versus the Day 1 scan.
- Overall agreement rate on the Day 0 and Day 1 scans, defined as the number lesions with matching subregion divided by the total number of lesions identified across all scans by either imaging.
- Overall agreement rate on the Day 0 and reference scans, defined as the number lesions with matching subregion divided by the total number of lesions identified across all scans by either imaging.
- Overall agreement rate on the Day 1 and reference scans, defined as the number lesions with matching subregion divided by the total number of lesions identified across all scans by either imaging.

#### 4.0 HYPOTHESIS TEST AND SAMPLE SIZE ESTIMATION

## 4.1 Hypothesis Test

No formal hypothesis testing is planned. All statistical testing and associated p-values are presented without controlling for the alpha level.

## 4.2 Sample Size Estimation

Approximately 50 participants are planned to be enrolled into the study. The assumed CDR of Cu-SAR-bisPSMA PET/CT imaging is 42% in this population. A sample size of 40 participants is estimated to provide more than 85% power to achieve a lower boundary of a 2-sided 95% exact binomial confidence interval (CI) about the estimated CDR that exceeds 20%. Accounting for a 20% non-evaluable rate, approximately 50 participants will need to undergo Cu-SAR-bisPSMA PET/CT in this study.

Additionally, for the co-primary efficacy endpoint of region-level PPV, assuming 65% of participants are estimated to have Cu-SAR-bisPSMA PET/CT positive findings in this target population and each participant with positive findings has an average of 1.3 positive regions, then 40 participants are expected to produce approximately 34 positive regions. The assumed region-level PPV rate of Cu-SAR-bisPSMA PET/CT imaging is approximately 65% in all PET positive regions. Therefore, a sample size of 40 participants (i.e., approximately 34 positive regions) is

September 4, 2024 CONFIDENTIAL Page 14 of 46

estimated to provide more than 80% power to achieve a lower boundary of a 2-sided 95% exact binomial CI about the estimated region-level PPV that exceeds 40%.

## 5.0 RANDOMIZATION AND BLINDING

This study is single-arm so there is no randomization.

There are multiple levels of blinding present in this study for the readers involved in determining PC from various imaging modalities, creating the composite reference standard, and evaluating the Cu-SAR-bisPSMA scans. Blinding will not be applied to the analysis as this is a single-arm study.

#### 6.0 ANALYSIS SETS

For the purposes of defining the analysis sets, a participant is considered enrolled when they have a Day 0 visit. Unless otherwise specified, data for participants who were enrolled but did not receive a Cu-SAR-bisPSMA administration will be listed but will not be included in summary tables. For purposes of analysis, the following analysis sets are defined:

Table 1 Analysis Sets

Analysis Set	Description	
All Participants Set	All screened participants who signed the informed consent form. Screen failure information will be summarized using the All Participants Set.	
Enrolled Analysis Set	All participants who signed the informed consent form (ICF) and were enrolled into the study. This will be used for patient disposition and analysis set summaries.	
Safety Analysis Set	All enrolled participants who receive any amount of  Cu-SAR-bisPSMA. This will be used to assess safety data.	
Full Analysis Set (FAS)	All participants who receive any amount of  Cu-SAR-bisPSMA and have  Cu-SAR-bisPSMA PET/CT imaging results from at least one central reader. This will be used for all efficacy analyses.	
Per Protocol (PP) Analysis Set	All participants in the FAS who have an evaluable assessment of the Reference standard against  Cu-SAR-bisPSMA PET/CT imaging results for the participant-level and at least 1 region for the Day 0 and Day 1  Cu-SAR-bisPSMA PET/CT scan and who	

September 4, 2024 CONFIDENTIAL Page 15 of 46

	have no exclusionary protocol deviations that exclude them from PP analysis. Participants that were replaced on study will not be included. This will be used to repeat the primary and selected secondary efficacy analyses only.
Biodistribution Analysis Set	All participants in the Safety Analysis Set who have at least one biodistribution measure. This will be used to summarize biodistribution data.

#### 7.0 STATISTICAL METHODS

#### 7.1 General Considerations

#### 7.1.1 Standard Calculations

- Variables requiring calculation will be derived using the following formulas:
- Baseline: A baseline value, unless specified otherwise, is the last non-missing value recorded prior to the Cu-SAR-bisPSMA administration. If an assessment has both a date and time that exactly match the date and time of first dose of study drug, the assessment will be counted as baseline. For participants who are enrolled, but not dosed, the last assessment collected on or prior to the enrollment date is considered baseline.
- Change from Baseline: Change from baseline will be calculated for each patient at the specified time point as the value at the specified time point minus the baseline value.
- Study Day: The day of Cu-SAR-bisPSMA administration will be on Day 0 as specified in the study protocol schedule of events, but for Clinical Data Interchange Standards Consortium (CDISC) compliance, the study day variables will consider this as "Day 1" as there cannot be a Day 0. Study listings will be presented as "Day 0" to match the protocol.
- For a given date, study day is calculated in the SDTM data as days since the date of single dose of Cu-SAR-bisPSMA:
  - Study day = date dose date + 1, where date  $\geq$  dose date
  - Study day = date dose date, where date < dose date
- For a given date, study day is calculated in the TLF presentations as days since the date of single dose of Cu-SAR-bisPSMA:
  - Study day = date dose date, where date  $\geq$  dose date
  - Study day = date dose date, where date < dose date
- Days: Durations, expressed in days, between one date (date1) and another later date (date2) are calculated according to the following formula: duration in days = (date2 date1 + 1).

September 4, 2024 CONFIDENTIAL Page 16 of 46

■ Body Mass Index (BMI): BMI  $(kg/m^2)$  = weight  $(kg) / [[height (cm)/100]^2]$ .

#### 7.1.2 Summarization Groupings

The summary tables will be presented by visit, timepoint (when applicable), and central reader (for efficacy analyses). As this is a single-arm study, only 1 group will be reported per analysis set.

## 7.2 General Comments on the Statistical Analyses

- Age will be computed from the informed consent date and the date of birth.
- Continuous variables will be summarized using number (n), mean, standard deviation (SD), median, 25th quartile, 75th quartile, minimum, and maximum.
- Categorical data will be reported with frequency counts and percentages.
- All relevant data captured on the electronic case report forms (eCRFs) and from external laboratories including specific descriptions of 'other' and comments fields will be provided in by-participant listings. All listings will be sorted by participant number and visit in ascending order.
- If a clinical laboratory result is reported relative to a lower/upper range of detection for an assay, for example, "<10", the numeric portion of the result (10) will be used for statistical analyses and the full result, including any symbols, will be provided in the patient listings.
- Analysis Data Model (ADaM) datasets will be prepared using CDISC ADaM Version 2.1 or later, and CDISC ADaM Implementation Guide Version 1.1 or later. Pinnacle 21 Community Validator Version 3.1.2 or later will be utilized to ensure compliance with CDISC standards.
- Version 9.4 (or higher) of the SAS® statistical software package will be used to provide all tables, listings, and figures.
- The analyses described in this plan are considered a priori, in that they have been defined prior to the first patient enrolled. Any changes to the planned analyses after first patient enrolled will be documented in this SAP and in the CSR.

## 7.3 Handling of Missing Data

- Missing values for individual data points will remain as missing. Missing values will not be imputed and only observed values will be used in data analyses and presentations unless otherwise indicated. For the reference standard, expert panel adjudications will never be missing and will be assigned as "non-evaluable" if based on missing data. Sensitivity analyses will be performed for non-evaluable reference standard assessments.
- Where individual data points are missing, categorical data will be summarized based on reduced denominators (i.e., only patients with available data will be included in the denominators) unless otherwise indicated.

September 4, 2024 CONFIDENTIAL Page 17 of 46

## 7.4 Reporting Conventions

In general, the units provided for a result will mirror what is collected on the eCRF unless otherwise specified. Results collected will use the number of decimal places that are collected, with mean, SD, and median reported to 1 decimal place greater than the original data. Minimum, maximum, 25th quartile and 75th quartile values will be reported to the same number of decimal places as the collected data.

P-values will be reported to 3 decimal places, with values less than 0.001 reported as "<0.001" and values greater than 0.999 reported as ">0.999".

## 7.5 Replacement of Participants

Participants who do not complete all required study visits (including those who receive prohibited treatment and are discontinued early) may be replaced if needed to achieve the target sample size. Participants who withdraw prior to receiving investigational product will be replaced.

The study team will meet periodically to determine if such participants need to be replaced.

## 7.6 Calculation of PSA Doubling Time and PSA Velocity

The following values of PSA are collecting for this study:

- PSA at Initial Diagnosis
- Nadir PSA after initial definitive treatment
- Most Recent PSA prior to screening #1 and #2
- Screening PSA
- PSA taken during the study at day 90 and 180 (if appliable) or after start of salvage focal therapy (can vary)

PSA doubling time (PSADT) and PSA velocity will be calculated at baseline and during the study and require different definitions. PSA at initial diagnosis will not be used for any calculations of PSA velocity or PSADT.

For calculation of PSADT and PSA velocity at **Baseline**, which will be calculated for all participants:

- PSA Velocity = Slope of the line of best fit using all available data within 12 months prior to screening as well as screening value (excluding at initial diagnosis).
- PSADT = ln(2) / ((ln(PSA value at screening) ln(oldest PSA value within 12 months prior to screening)) / (# of months from oldest PSA value within 12 months prior to PSA at screening))

September 4, 2024 CONFIDENTIAL Page 18 of 46

For calculation of PSADT and PSA velocity for on-study measurements, only the last measure of PSA taken during the study will be used. The following calculations will be done for PSA measurements **Post-Baseline**:

- PSA Velocity = Slope of the line of best fit using all available data on-study, including screening value.
  - o If the participant initiated radiation therapy on-study, the last PSA value is instead the last PSA value PRIOR to initiating radiation therapy.
- PSADT = ln(2) / ((ln(Last on-study PSA value) ln(PSA at screening)) / (# of months from last on-study PSA value to PSA at screening))
  - o If the participant initiated radiation therapy on-study, the last PSA value is instead the last PSA value PRIOR to initiating radiation therapy.
- If a participant has no post-screening value prior to initiation of radiation therapy, they will be excluded from post-baseline calculations of PSADT and PSA velocity.

For the calculation of the line of best fit for PSA Velocity, the following equations will be used for each participant, where  $x_i$  is the date of the measurement in months from screening (screening is x = 0) for each value,  $y_i$  is the PSA value, and n is the total number of datapoints for the participant for that calculation:

$$\overline{X} = \frac{\sum_{i=1}^{n} x_i}{n} \quad \overline{Y} = \frac{\sum_{i=1}^{n} y_i}{n}$$

$$PSA \ Velocity = \frac{\sum_{i=1}^{n} (x_i - \overline{X})(y_i - \overline{Y})}{\sum_{i=1}^{n} (x_i - \overline{X})^2}$$

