7.2.6 Clinical Laboratory Assessments

Clinical laboratory samples will be analyzed by the site's local laboratory.

Blood samples will be collected for the following tests:

- Hematology: Hemoglobin, hematocrit, red blood cell count, white blood cell count (WBC), platelet count, differential WBC (neutrophils, eosinophils, basophils, lymphocytes, and monocytes), absolute neutrophil count, and absolute lymphocyte count.
- Biochemistry (pre-prandial): albumin, total protein, blood glucose, sodium, potassium, blood urea nitrogen, creatinine, calcium, uric acid, AST, ALT, total bilirubin, alkaline phosphatase.
- Coagulation: prothrombin time, activated partial thromboplastin time, D-dimer. *Note: Coagulation may be assessed at any other timepoint, outside of those specified in the Schedule of assessments, in case of an abnormal result, and followed until resolution.*
- eGFR: will be calculated from creatinine using the Chronic Kidney Disease Epidemiology Collaboration (CKD-EPI) formula and reported as mL/min. To convert mL/min/1.73 m2 to mL/min, multiply by the individual's Body Surface Area (calculated using the Mosteller formula) and divide by 1.73.
- Biochemical Markers: Serum testosterone.

Urine samples will be collected for the following tests:

• Urinalysis: to include determination of protein, glucose and leukocytes (dipstick test).

In the event of an unexplained, clinically significant abnormal laboratory test result, the test should be repeated and followed up until it has returned to the normal range and/or an adequate explanation of the abnormality is found.

During the study, all out of range (abnormal) laboratory values, except for PSA, must be evaluated and commented on by the Investigator (or a qualified delegated observer at the investigational site) for clinical significance using one of the following categories: within normal limits, abnormal but not clinically significant, or abnormal and clinically significant. Clinically significant observations will be recorded as AEs unless they are associated with a diagnosis that itself has been reported as an AE (e.g., raised white cells and fever associated with an infection – in this case the infection is the AE and the lab value and fever are signs and symptoms of the AE and should not be reported separately).

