7.2.7 Total PSA

As part of Screening, baseline PSA will be assessed; additionally, PSA results and dates of 2 previous most recent measurements (prior measurements are needed to assess PSA velocity/doubling time), PSA at initial diagnosis and PSA after initial definitive treatment (nadir) must also be recorded on the eCRF.

Prostate-specific antigen will further be assessed during the Follow-Up as specified in the Schedule of assessments. However, if radiation therapy or other salvage focal therapy (e.g., cryotherapy) is initiated during the study (as long as no concomitant ADT is given), PSA levels must be monitored every 4 weeks from the initiation of the therapy. Prostate-specific antigen response (defined as total PSA decline by \geq 50% from baseline) must be confirmed by a second value within 4 weeks.

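### Baseline PSADT may start from an undetectable PSA entered at the local assay limit, so for some men the exploratory PSADT bin depends partly, and at low limits mainly, on that limit

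*SAP*

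**What the plan says.** SAP 7.6 lists the PSA values collected: at initial diagnosis, "Nadir PSA after initial definitive treatment", the two most recent before screening, at screening, and on study. It then rules out one of them: "PSA at initial diagnosis will not be used for any calculations of PSA velocity or PSADT". Nothing there removes the nadir or an undetectable value.

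Baseline PSADT, "which will be calculated for all participants", is a two-point log formula. The later point is the screening PSA and the earlier point is the "oldest PSA value within 12 months prior to screening". Baseline PSA velocity is a least-squares slope through all values in the same window.

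For results given relative to a detection limit, SAP 7.2 uses <10 as its example and says that "the numeric portion of the result (10) will be used for statistical analyses". Protocol 7.2.6 states: "Clinical laboratory samples will be analyzed by the site's local laboratory". Neither document sets a common PSA assay or reporting limit.

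Protocol 7.2.7 asks for the two most recent earlier PSA results with their dates because "prior measurements are needed to assess PSA velocity/doubling time". It adds that "PSA after initial definitive treatment (nadir) must also be recorded on the eCRF".

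SAP 9.14.3.2 then summarizes CDR, PPV and DR by baseline PSADT in four bins: under 3.0, 3.0–8.9, 9.0–14.9, and 15.0 months or more.

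**The concern.** If the nadir lies within 12 months of screening, it would normally precede the two recent rising values and so become the earlier point. If it was undetectable, the value used is the laboratory's reporting limit and not a measured concentration. The two recent values that the protocol collects for this purpose then drop out of the PSADT formula.

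Two men with the same PSA course but different local assays could then be placed in different PSADT bins. Any relation between PSADT and detection would be blurred by a laboratory characteristic. A nadir entered as 0 would leave the logarithm undefined, and the SAP has no rule for that.

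**Working it through.** The documents give no worked PSADT, so there is no stated figure to reproduce. The check applies the SAP 7.6 formula to an assumed history.

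**Inputs from the documents.** The formula is in SAP 7.6, the less-than rule in SAP 7.2, and the bins in SAP 9.14.3.2.

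**Assumptions (not in the documents).** Undetectable PSA 11 months before screening; PSA 0.20 and 0.28 ng/mL at 4 and 2 months before; 0.40 ng/mL at screening; reporting limit L of 0.01, 0.1 or 0.2 ng/mL.

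**Step 1: SAP formula with the undetectable value set to L.** PSADT = ln(2) × 11 / ln(0.40/L), with ln(2) × 11 = 7.625.

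| L (ng/mL) | ln(0.40/L) | PSADT (months) | Bin (months) |
|---|---|---|---|
| 0.01 | 3.689 | 2.07 | under 3.0 |
| 0.1 | 1.386 | 5.50 | 3.0–8.9 |
| 0.2 | 0.693 | 11.00 | 9.0–14.9 |

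**Step 2: detectable values only.** The two-point formula from 0.20 to 0.40 over 4 months gives ln(2) × 4 / ln(2) = 4.0 months. The least-squares slope of ln(PSA) on months through the three detectable values is ln(2)/4, which also gives 4.0 months. This falls in the 3.0–8.9 bin whatever the limit.

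**Step 3: does growth still count?** With an assumed 10-month interval and L = 0.1, PSADT is 10.0 months at a screening PSA of 0.2, 4.3 at 0.5 and 2.3 at 2.0, which spans three bins. With L = 0.01, the same range of screening PSA gives 2.3 down to 1.3 months, all in the lowest bin. Growth therefore still matters, but at a low limit the bins stop separating these men.

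**Step 4: is the example unusual?** The formula was run on 81 assumed histories (screening PSA 0.2 to 2.0 ng/mL, interval 4 to 12 months). Moving L from 0.1 to 0.01 changes the bin in 47 of 81 (58%). This shows that bin changes do not need a special case. It is not an estimate of how often they occur in this trial.

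**Step 5: baseline velocity.** For the Step 1 history, the SAP slope in ng/mL per month multiplied by 12 is 0.40 ng/mL/y at L = 0.01, 0.30 at L = 0.1 and 0.18 at L = 0.2. The detectable values alone give 0.60. The top velocity bin in SAP 9.14.3.2 starts at 0.20, so only L = 0.2 changes the bin.

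**Direction.** The true undetectable value is at or below L, so entering L gives an upper bound on the two-point PSADT. That two-point figure also spans the undetectable period, so it does not measure growth after the rise began.

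**The case against.** A reader might infer that PSADT reflects the assay limit and not PSA growth. The documents do not support that. The formula always contains the screening PSA and the elapsed time, and Step 3 shows that both move the result.

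A reader might also infer that the problem is general. It is not shown to be. It needs the oldest value in the 12-month window to be undetectable. If the nadir is older than that, the earlier point is one of the two recent PSAs, which may be detectable. Neither document says how often the nadir is undetectable or recent.

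Two links in the chain are readings and not statements. SAP 7.2 speaks of clinical laboratory results and does not say that it covers a historical PSA entered on the eCRF. Protocol 7.2.7 explicitly asks for dates only for the two recent PSAs, and a nadir without a date could not be placed in the window. Both points stand as limits. Even so, the SAP gives no other rule for a less-than PSA, and it excludes the diagnostic value by name while leaving the nadir in.

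The three-bin spread in Step 1 needs an assumed limit of 0.2, which equals the post-prostatectomy entry threshold in Protocol 4.1.1. Without that row the same man spans two bins, and at L = 0.1 he is in the same bin as his detectable values. The velocity effect is weak: at limits of 0.1 or below, the example stays in the top bin.

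Finally, PSADT is one of nine variables in an exploratory summary by reader. SAP 4.1 plans no formal hypothesis test, and SAP 9.14.3.6 lists all PSA and PSADT values, so odd values can be seen. That limits the consequence but does not correct the rule.

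**Conclusion.** The concern holds in a limited form and is minor. As written, the SAP lets an undetectable PSA serve as the earlier point of baseline PSADT at the local reporting limit. For men whose oldest value in the window is undetectable, the result depends partly on that limit, and mainly on it when the limit is low. In the example the limit alone moves PSADT from 2.1 to 5.5 months and across a bin boundary, against 4.0 months from the detectable values.

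This rests on the assumed PSA history and assay limits, on SAP 7.2 applying to historical PSA, and on the nadir having a usable date. The number of men affected is unknown. A reversal of the relation between PSADT and detection is not shown. Only exploratory results that use baseline PSADT, and to a lesser degree baseline velocity, are exposed. Primary CDR and PPV are not affected.

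**What to change.** Amend SAP 7.6 as follows:

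- PSA results reported as below a limit, or as 0, are not used for baseline PSADT.
- Baseline PSADT uses the screening PSA and the detectable values within the preceding 12 months, from the nadir onward. A detectable nadir is a real measurement and may be kept.
- Preferably, PSADT is ln(2) divided by the least-squares slope of ln(PSA) on months. The two-point formula on the same values gives the same answer in the example; regression has the advantage of using every value.
- PSADT is missing if fewer than two values remain.
- A zero or negative slope is reported as a separate category.
- Baseline PSA velocity uses the same values, for consistency.

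The cost is SAP wording and a few lines of code. SAP 1.0 already provides for an SAP amendment before database lock. The downside is that some men will have a missing PSADT. Post-prostatectomy eligibility requires a PSA of at least 0.2 ng/mL and a confirmatory value at the same level, so two detectable values should exist for those men, although not necessarily within 12 months.

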6.2 Permitted Treatments

All SOC treatments are permitted throughout the duration of the participant's involvement in the study with the exception of those treatments outlined in Section 6.3.

6.3 **Prohibited Treatments**

Treatment with investigational agents (that are likely to affect PSA levels or antineoplastic agents), saw palmetto, estrogens, steroids, testosterone supplements, 5ARIs (finasteride/dutasteride), and any antineoplastic therapy (with the exception of radiation or other salvage focal therapy with no concomitant ADT initiated following completion of Visit 4) is prohibited throughout the duration of the participant's involvement in the study.

Histopathological confirmation of PC prior to commencement of radiation or other salvage focal therapy is strongly encouraged.

Participants who receive prohibited treatment(s) should remain in the study until completion of Visit 4 to enable the assessment of safety.

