#### 9.14.3.6 PSA Measures Change from Baseline

Total PSA, PSA velocity, and PSADT levels will be summarized descriptively at each timepoint including a change from baseline. Boxplots showing the mean, median, Q1, Q3, and outliers for each PSA measure will be presented for each timepoint to investigate PSA over time.

Additional summaries of total PSA, PSA velocity, and PSADT levels will be presented for the following subgroups:

- Participants who received salvage focal therapy
- Participants who were TP for the primary analysis at the participant-level
- Participants who were FP for the primary analysis at the participant-level
- Participants who were TN for the primary analysis at the participant-level

All PSA, PSA velocity, and PSADT levels will be listed.

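### SAP 7.6 cuts off on-study PSADT and PSA velocity at radiation therapy only, so PSA after other permitted salvage focal therapy enters these exploratory measures

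*SAP*

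**What the plan says.** SAP 7.6 sets a default for on-study PSA and one exception.

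- **Collected values.** The list includes "PSA taken during the study at day 90 and 180 (if appliable) or after start of salvage focal therapy (can vary").
- **Default.** The section opens by saying that "only the last measure of PSA taken during the study will be used". PSADT compares that value with the screening PSA. Velocity is the "Slope of the line of best fit using all available data on-study, including screening value".
- **Exception, stated under both measures.** "If the participant initiated radiation therapy on-study, the last PSA value is instead the last PSA value PRIOR to initiating radiation therapy".
- **Exclusion.** "If a participant has no post-screening value prior to initiation of radiation therapy, they will be excluded from post-baseline calculations" of PSADT and velocity.

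The protocol permits more than radiation. Protocol 6.3 prohibits antineoplastic therapy on study "with the exception of radiation or other salvage focal therapy with no concomitant ADT initiated following completion of Visit 4". Protocol 3.1 and 7.2.7 give cryotherapy as the example of other salvage focal therapy and require PSA every 4 weeks from the start of either kind.

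SAP 9.14.3.6 summarises PSA, velocity and PSADT overall and for four subgroups: TP, FP and TN participants, and "Participants who received salvage focal therapy". Protocol 10.4.5.3 lists on-study PSADT and velocity as exploratory, with descriptive statistics only.

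**The concern.** Two therapies that the protocol permits on the same terms are handled by different rules. After radiation, PSADT falls back to the last pre-treatment PSA. After cryotherapy or another focal therapy the default applies, so PSADT uses a post-treatment PSA and velocity uses every post-treatment PSA. The 4-weekly sampling means that such values will normally exist.

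The wording is not obviously shorthand. The same section recognises PSA taken after salvage focal therapy in general. SAP 7.8 treats radiation and other salvage focal therapy alike when it defines confirmed PSA response. SAP Table 3 gives no reason for a difference.

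At stake is whether the tables can be read. A post-treatment fall gives a negative doubling time. Protocol 6.3 treats radiation as one kind of salvage focal therapy, so on that reading the salvage subgroup pools pre-treatment values (radiation) with post-treatment values (other therapy). The TP subgroup is exposed too, because a PSA response to focal therapy can itself make a PET-positive participant TP.

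**Working it through.** The documents give no figure to reproduce. The check applies the SAP 7.6 formulas to one PSA course under each rule.

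**Formulas.** With screening PSA P0 and last PSA P1, T months apart, PSADT = ln 2 / ((ln P1 - ln P0)/T). Velocity is the least-squares slope of PSA on months, multiplied by 12 here to give ng/mL/year.

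**General result.** If P1 is exactly half of P0, the denominator is -ln 2/T and PSADT = -T. A larger fall gives a value between -T and 0. A 50% fall from baseline is the plan's own response threshold (SAP 7.8). Taking baseline as the screening PSA, any non-radiation responder whose last value stays at or below that threshold has a negative PSADT.

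**Simple case (assumed).** A fall from 1.0 to 0.4 ng/mL over 6 months gives ln 2 / ((ln 0.4 - ln 1.0)/6) = -4.5 months.

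**Side-by-side case (all values assumed).** Screening PSA is 1.0 ng/mL and the untreated doubling time is 9 months. Focal therapy starts just after Day 90. PSA is then taken at Days 118, 146 and 174, and one month is 30.4375 days.

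- Day 90 is 2.957 months, so PSA is 2^(2.957/9) = 1.256.
- Day 174 is 5.717 months, with PSA 0.5. Day 146 is also 0.5, and Day 118 is midway between 1.256 and 0.5, at 0.878.

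| | Cut-off applied (radiation) | Default applied (other focal therapy) |
|---|---|---|
| PSADT | ln 2 / (ln 1.256/2.957) = 9.0 months | ln 2 / (ln 0.5/5.717) = -5.7 months |
| Velocity | slope through 2 points = +1.04 | slope through 5 points = -1.23 |

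The radiation velocity assumes that the rule removes every post-treatment value from the slope. The SAP does not expressly say so: it replaces the last value, while the slope uses all on-study data. If velocity instead used only screening and last PSA, the default would give (0.5 - 1.0)/5.717 x 12 = -1.05, still negative.

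**Range.** For last PSA 30% to 80% below screening, default PSADT runs from -11.1 to -2.5 months. Default velocity runs from -0.75 to -1.93 at the 9-month doubling time. For untreated doubling times of 6 to 12 months, the cut-off gives PSADT of 6.0 to 12.0 months and velocity of +1.65 to +0.76. The deeper fall gives the PSADT nearer zero, so negative and positive values do not share a meaningful scale for averaging.

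**Effect on an overall mean (assumed).** Suppose 40 participants contribute, all others at 9 months, with k at -5.7 months. The mean is ((40 - k) x 9 + k x (-5.7))/40, which is 8.6, 8.3, 7.5 and 6.1 months for k = 1, 2, 4 and 8. The documents give no basis for choosing k, and it may be zero.

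**The case against.** The strongest case against concerns reach. On-study PSADT and velocity are exploratory and descriptive, and SAP 4.1 plans no formal testing. They do not feed CDR, PPV, detection rate or TP/FP assignment. The baseline-variable analyses in SAP 9.14.3.2 use baseline PSADT and velocity, which are derived separately. All of this stands.

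Treated participants also remain identifiable: SAP 9.14.3.6 gives the salvage subgroup its own summary and lists all values, and SAP 9.9 lists treatments with dates. That helps a reader of the listings. It does not change the derivation, remove these participants from the overall and TP summaries, or stop the salvage subgroup itself being mixed.

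A reader might infer several stronger claims that the documents do not support:

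- **That the measures are meant to describe untreated PSA kinetics.** No section says so. Protocol 10.4.5.3 asks only for values at baseline and at end of study. The purpose can be inferred from the radiation cut-off, but what the text establishes is unequal handling without a stated reason.
- **That PSA after salvage node dissection is caught in the same way.** Protocol 7.4 mentions this surgery only as a source of histopathology. Whether it counts as salvage focal therapy is not stated.
- **That systemic therapy is an equal problem.** Antineoplastic systemic therapy is prohibited. Protocol 4.4.4 and SAP 7.5 foresee early discontinuation and possible replacement of such participants, so later PSA may often not exist. SAP 7.6 has no rule for it, but nothing shows that it matters here.
- **That the change costs nothing.** Focal therapy may start after Visit 4 (Day 7), whereas the first scheduled post-screening PSA is at Day 90. Extending the exclusion bullet removes participants treated in between.

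**Conclusion.** The point holds as a gap in a derivation rule, with limited consequences. Read literally, SAP 7.6 puts post-treatment PSA into on-study PSADT and velocity after non-radiation salvage focal therapy, while PSADT after radiation stops at the last pre-treatment value. In the assumed course this moves PSADT from 9.0 to -5.7 months and velocity from +1.04 to -1.23 ng/mL/year. The sign change does not depend on the exact figures: any last PSA below screening gives a negative PSADT.

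The overall, TP and salvage-focal-therapy summaries in SAP 9.14.3.6 are affected; no primary or secondary efficacy result is. The size in the actual data depends on how many participants receive non-radiation focal therapy, which the documents do not give. The correction is worth making because it is small and the salvage subgroup otherwise has no single interpretation.

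**What to change.** In SAP 7.6:

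1. In the two cut-off bullets and the exclusion bullet, replace *radiation therapy* with *radiation or other salvage focal therapy*.
2. For velocity, state that only PSA values before the first start date of that therapy enter the slope. The phrase change alone would not expressly drop later values. Reconcile this with the opening sentence, which limits on-study calculations to the last PSA.

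No new data are needed: Protocol 7.1.4 already records treatment start dates on the eCRF. Under SAP 1.0 the change needs an SAP amendment. The analytic cost is that participants who start focal therapy before their first post-screening PSA, normally Day 90, leave post-baseline PSADT and velocity, as radiation participants already do. Report the number excluded for this reason beside the overall and salvage-focal-therapy summaries.
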